7.1.4 Pre-specified Protocol Deviations and Flow Chart of Analysis Population Set Determination

The following pre-specified protocol deviation items will be checked according to the principle of statistical analysis by SAS programming. These items may be a little bit different from the protocol deviations reported by clinical operation which are collected by CRF.

(1) Withdrawal of informed consent: Subjects obtain registration number, but do not end up using the study device. These are subjects who have had no exposure to the study device (i.e., no Successful or Unsuccessful Implant form is completed).

(2) Violation of inclusion and exclusion criteria: Subjects do not meet the inclusion criteria set in the protocol or meet the exclusion criteria set in the protocol, and this protocol deviation may severely affect the results of primary endpoint. Whether protocol deviation severely affect the results of primary effective endpoints shall be judged together by sponsor, investigators and statistician through discussion at a final data review meeting prior to final database lock.

(3) Lost to follow-up : Subjects are unable to obtain the primary endpoint (i.e. the primary endpoint is identified as true missing). If a subject has a primary endpoint failure, and later is lost to follow-up (prior to 183 days), the subject will still be included in the primary endpoint analysis. This criterion will only be used for the primary endpoint.

(4) Out of time window: The difference between the 6-month follow-up date after operation and operation date of subjects is less than 183 days and this may severely affect the results of primary endpoint. Whether protocol deviation severely affects the results of primary endpoint will be judged together by sponsor, investigators and statistician by discussion at the final data review meeting prior to final database lock. If a subject has a primary endpoint failure, and later has the 6 month visit too early (prior to 183 days), the subject will still be included in the primary endpoint analysis.

(5) Application of Non-study devices: The device implanted for subject is not the study device specified in study protocol or the subject ended up receiving no device at all. If a subject has a primary endpoint failure during the unsuccessful implant attempt, the subject will still be included in the primary endpoint analysis.

[figure not shown]
FAS= Number of the enrolled patients – Number of patients who withdraw informed consent;

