PPS=FAS – Number of patients who severely violate study protocol;

Number of patients who severely violate study protocol = Number of patients who violate inclusion and exclusion criteria + Lost to follow-up + Number of patients with out of time window + Number of patients with application of Non-study devices

Priority level of severely violating study protocol: Lost to follow-up, application of non-study devices, violation of inclusion and exclusion criteria, out of time window. If subjects meet two or more above severe cases of protocol deviation, they will be classified in accordance with above priority level of protocol deviation.

The serious protocol deviations of subjects will be listed based on actual cases after final data review meeting determination. (For example, if the number of subjects who are out of time window is 0, this item will not be displayed in the table). Additionally, the subjects who were withdrawal of informed consent or serious protocol deviations will be listed, including the center number, registration number, gender, age, deviation type, deviation reason, FAS and PPS.

Figure 2: Flow Chart of Analysis Population Set Determination

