A Kaplan-Meier survival analysis will be conducted to estimate the freedom from AEs classified as major complications that are related to the Micra TPS and/or procedure by the CEC within 6-months (183 days) post-implant. The Kaplan-Meier method is an appropriate method to analyze this endpoint as it enables inclusion of all subjects with an attempted implant. Additionally, the onset date of all Micra related major complications will be known to the nearest calendar day. Day of follow-up for subjects successfully implanted with the Micra TPS will be calculated as the minimum of the days from successful implant to: (1) onset date of a major complication related to the Micra TPS or procedure (if any), (2) study exit date (if exited), (3) death date (if death occurs), (4) 6-month follow-up visit (if completed), (5) last follow-up visit, or (6) 184 days. Subjects without a major chronic complication related to the Micra TPS and/or procedure during the follow-up period will be considered censored in the Kaplan-Meier analysis. Days of follow-up for subject who have only unsuccessful implant attempt(s) without being successfully implanted will be set to zero (0), unless a major complication occurs in which case the days of follow-up will be calculated from the date of unsuccessful implant attempt to the event onset date. The null hypothesis will be rejected in favor of the alternative if the lower boundary of the two-sided 95% CI is greater than 83%.

The 6-month (183 day) major complication freedom rate will be estimated using the Kaplan-Meier method with the log-log transformation to compute the two-sided CIs, [REDACTED]

[REDACTED]

[REDACTED]

[REDACTED]

Additionally, a corresponding one-sided p-value comparing the 6-month Micra procedure and/or system major complication freedom rate to 83% will be constructed using the formula:

$$z = \frac{\log(-\log(S(t))) - \log(-\log(0.83))}{\sqrt{\sigma(t)^2 / (S(t) * \log(S(t)))^2}}$$

Where $S(t)$ is the observed 6-month (183 days) freedom rate and $\sigma^2(t)$ is Greenwood's estimate of the variance of the survival function at time t . The one-sided p-value will then be computed from the standard normal distribution as $P(Z < z)$ [note this is the area of the standard normal distribution less than z since $\log(-\log(S(t)))$ will be more negative than $\log(-\log(0.83))$ if $S(t) > 0.83$].

[REDACTED]

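### SAP 7.1.4 lets the outcome decide who stays in the per-protocol set for the primary analysis, and item (5) can drop a known procedural failure from that set

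*SAP*

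**What the plan says.** SAP 7.1.3 runs the primary objective on both the FAS and the PPS. SAP 7.1.4 forms the PPS by subtracting severe violators from the FAS, counted as "Number of patients who violate inclusion and exclusion criteria + Lost to follow-up + Number of patients with out of time window" plus those with a non-study device or no device.

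Three of the items treat failures differently from event-free subjects:

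- **Item (3), lost to follow-up.** The exclusion reads "Subjects are unable to obtain the primary endpoint (i.e. the primary endpoint is identified as true missing". The exception is "If a subject has a primary endpoint failure, and later is lost to follow-up (prior to 183 days), the subject will still be included". The item adds: "This criterion will only be used for the primary endpoint".
- **Item (4), 6-month visit before day 183.** Exclusion follows if a meeting before database lock judges the effect on the primary endpoint severe. The exception begins "If a subject has a primary endpoint failure, and later has the 6 month visit too early (prior to 183 days".
- **Item (5), another device or no device.** The exception is "If a subject has a primary endpoint failure during the unsuccessful implant attempt, the subject will still be included in the primary endpoint analysis".

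SAP 7.9.1.2 defines follow-up time twice. Its Definitions list runs follow-up to the onset of a related major complication, and uses the last follow-up date only if nothing else on the list occurs. A later paragraph takes the minimum of several times, among them "4) 6-month follow-up visit (if completed), (5) last follow-up visit, or (6) 184 days". For a subject with only unsuccessful attempts it sets follow-up to zero, with one exception for those who have a major complication; for them the text reads: "in which case the days of follow-up will be calculated from the date of unsuccessful implant attempt to the event onset date". SAP 7.9.1.4 keeps discontinued subjects up to their censoring date.

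**The concern.** Two subjects with the same deviation can be treated differently because one of them had an event. An event-free subject can leave the PPS, while a subject who failed first stays. A supportive analysis should show whether deviations change the conclusion. This one can differ from the FAS through its selection rule alone.

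The removal is also unnecessary. Kaplan-Meier already uses incomplete follow-up, and SAP 7.9.1.2 and 7.9.1.4 already censor these subjects in the FAS.

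Item (5) can err the other way. A procedural complication may start after the attempt has ended, and Protocol 10.1.3.1 allows unimplanted subjects to remain in the study for up to 30 days, longer if a related adverse event is identified. SAP 7.9.1.2 counts such a complication at its onset date. Read literally, item (5) does not protect that subject, so a known failure on a safety endpoint counts in the FAS and is missing from the PPS.

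**Working it through.** **Inputs.** Kaplan-Meier at 183 days with log-log two-sided 95% limits, pass if the lower limit exceeds 83% (SAP 7.9.1.1, 7.9.1.2). Expected rate 94%, attrition 10%, 82 enrolled (SAP 6.1, 6.2). 719 implanted from 725 attempts in the global study (SAP 3).

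**The plan's own figure.** [1.96·√(0.83·0.17) + 0.8416·√(0.94·0.06)]² / 0.11² = 72.42, rounded up to 73; 73/0.9 = 81.1, rounded up to 82. Reproduced.

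**Direction, items (3)-(4).** The estimate is the product of (1 − dᵢ/nᵢ) over event times. Removing a censored subject can only reduce nᵢ, and every dᵢ stays. The estimate falls, or is unchanged if the subject was censored before every event. In 20,000 random data sets where only censored subjects were removed, neither the estimate nor the lower limit ever rose (estimate unchanged in 3,329).

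**Exception, item (4).** Take 82 subjects, four early failures, and one subject with the 6-month visit on day 175 who fails on day 180.
- Definitions list: the failure counts. FAS 5/82 = 93.9% (lower limit 85.97%). Dropping the subject gives 4/81 = 95.1% (87.38%), a rise.
- Minimum rule: the subject is censored on day 175. FAS 95.12% (87.52%); PPS 95.06% (87.38%), a fall.

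**Lower limits.** With d failures among n and all failures before any censoring, S = 1 − d/n, se = √[d/(n(n−d))] / |ln S|, and lower limit = S^exp(1.96·se). For 6/82: S = 0.9268, √[6/(82·76)] = 0.03103, |ln S| = 0.07599, se = 0.408, lower limit 0.8444.

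| Failures/n | Lower limit | Result |
|---|---|---|
| 7/82 | 82.93% | fail |
| 6/82 | 84.44% | pass |
| 6/81 | 84.25% | pass |
| 6/75 | 83.06% | pass |
| 6/74 | 82.84% | fail |
| 5/82 | 85.97% | pass |
| 5/68 | 83.23% | pass |
| 5/67 | 82.996% | fail |

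With 6 failures, 82 − 74 = 8 event-free removals reverse the PPS result. With 5 failures, 82 − 67 = 15 are needed.

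**How often items (3)-(4) might matter.** Simulation with 82 subjects and a true rate of 94%. Event and loss timing, and the share of event-free losses treated as true missing (25%, 50%, 100%), are assumptions; the documents give none of them. Every removal is of an event-free subject, so the downward direction is built in. Cells show bias in percentage points, then the chance that the FAS passes and the PPS fails.

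| Loss | 25% removed | 50% removed | 100% removed |
|---|---|---|---|
| 2% | 0.02-0.03; 0% | 0.03-0.05; 0% | 0.06-0.12; 0% |
| 5% | 0.04-0.07; 0% | 0.08-0.14; 0-0.2% | 0.16-0.29; 0.4-0.8% |
| 10% | 0.08-0.14; 0-0.6% | 0.16-0.29; 0.4-2.1% | 0.33-0.61; 6.2-7.8% |

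The 10% row is an upper scenario, because the plan's 10% is total attrition. For early visits (assumed on days 169-182, all removed): 2% of subjects gives 0.11-0.12 point and no reversal; 5% gives 0.29-0.30 point and 0.6-0.7% reversals.

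**Item (5).** From 7/82 (82.93%, fail), dropping one later-onset failure gives 6/81 (84.25%, pass). One such drop changes the result only when the FAS has exactly 7 failures, about 10% likely at a true rate of 94% and 3% at 96%. Expected unsuccessful attempts: 82·6/725 = 0.68; chance of at least one: 1 − (1 − 6/725)^82 = 49%. The documents do not say how often a later-onset major complication follows one.

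**The case against.** The retention clauses protect the safety endpoint: they stop observed failures from being discarded, and a subject who failed plainly has an observed endpoint. True missing is illustrated only by permanently lost adverse-event data with an inconclusive CEC review (SAP 7.4, 7.9.1.4), so an ordinary loss may never meet item (3). A subject who does match that example has an unresolved event, so calling that subject event-free is itself an assumption. Item (4) needs a judgement before lock. Protocol 14.1.9 and SAP 7.9.1.3 name the FAS for the primary objective. The item (5) case needs several uncommon things together.

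All of this bears on size, and it stands: few subjects may be affected. It does not remove the dependence on outcome, or the conflict between item (5) and SAP 7.9.1.2. Keeping failures is right; the fault is removing comparable event-free subjects when censoring would serve.

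Three stronger readings are tempting, and the documents do not support them:

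- A reader might infer that items (3)-(4) can only lower the PPS estimate. That holds under the minimum rule, but not under the Definitions list for a failure after an early visit.
- A reader might infer that every loss leaves the PPS. The true-missing wording does not say so.
- A reader might infer that the trial's pass/fail result is biased. The FAS keeps all these subjects, although SAP 7.1.3 does not say which set decides if the two disagree.

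**Conclusion.** Wrong as written, minor in consequence. PPS membership for the primary analysis depends on outcome. Items (3)-(4) work against the device under the minimum follow-up rule. Item (5) read literally, and item (4) under the Definitions list, can work in its favour by dropping a known failure.

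The effect is probably small. At 5% loss the simulated bias is at most 0.29 point and the chance of a PPS reversal at most 0.8%, even if every event-free loss is removed. These sizes rest on a true rate of 94%, 82 subjects and assumed timing. The item (5) example shows what one dropped failure can do, and its probability cannot be derived from the documents.

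**What to change.** Change the SAP wording, for the PPS primary analysis only:

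- **Items (3)-(4):** do not exclude lost or early-visit subjects. Censor event-free ones at last follow-up, as SAP 7.9.1.2 and 7.9.1.4 do for the FAS, and leave true missing data to the sensitivity analyses in 7.9.1.4.
- **Items (4)-(5):** keep any subject with a CEC-adjudicated primary endpoint failure through day 183, whether it came before or after an early visit, or during or after an unsuccessful attempt.
- **SAP 7.9.1.2 and 7.1.3:** reconcile the two follow-up definitions so that a failure after an early visit is handled in one way. Counting it fits the endpoint in SAP 4.1, which runs to day 183. State that the FAS decides pass/fail and the PPS is supportive.

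Event-free subjects who received no device may stay excluded. Censored at day 0, they can matter only for events on day 0 itself: with two such subjects and four failures, one of them on day 0, the estimate is 95.03% with them and 95.00% without.

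The change needs no new data and alters neither the sample size nor the choice of the FAS; settling the follow-up definition only makes explicit how the FAS treats a failure after an early visit. The cost is a PPS closer to the FAS, although the eligibility exclusions in item (2) still separate them.

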7.2 General Methodology

After the study planning phase, the Leading Institution authorized statistician(s) will take responsibilities for statistical activities relevant to statistical analyses that will be used for China Food and Drug Administration (CFDA) submissions. All statistical analyses for the clinical study

report will be carried out and validated by the Leading Institution authorized statistician(s). The Medtronic statistician or designee will continue to be involved in the activities for quality control and provide consultation to study execution (as per Medtronic Guidelines for Statistical Activities Related to Medtronic-Sponsored Pre-Market Human Clinical Studies in China, version 2.0). The Medtronic statistician or designee will be responsible for all publication related statistical activities.

7.3 Center Pooling

The study will enroll 82 subjects from 7 investigational sites in China. The maximum enrollment number from a single site should not exceed 50% of the total enrollment size. Centers will be pooled for all analyses of study objectives.

7.4 Handling of Missing, Unused, and Spurious Data and Dropouts

Data entry error or non-reasonable values will be cleaned before data analysis. In the event of subject exit or withdrawal of consent, the subject's data collected prior to study exit will still be included in the final statistical analysis. The specific reasons for subject exit or withdrawal will be provided in detail in the study report. If no data can be collected from a subject during post-implant follow-up, additional sensitivity analyses may be performed.

This study will use the survival analysis method for the primary objective. The Worst-Case Scenario Analysis will only be performed if it is identified as a true missing (e.g. permanent missing of AE-related data, and subsequently resulting in non-conclusive CEC review). The sensitivity analysis may count such missing data as failures.

Study subject disposition will be reported. Subjects visits will be tabulated, and compliance to study protocol required visit schedule will be summarized. Protocol deviations will be required for all missed visits and/or incomplete or incorrect data collection. The main analysis of the study primary objective will be based on available data and missing data will not be imputed. However, additional sensitivity analyses will be done to assess the potential impact of missing data. Refer to section 7.9.1.4 for further details.

7.5 Adjustments for Multiple Comparisons

No adjustments are planned for multiple comparisons.

7.6 Demographic and Other Baseline Characteristics

Baseline characteristics and relevant medical history will be collected on eCRFs for all enrolled subjects. Baseline characteristics will be summarized for all enrolled subjects. Baseline variables to be summarized include, but are not limited to: age, sex, race, height, weight, left ventricular ejection fraction (LVEF), pacing indication, arrhythmia history, medical and surgical history, and baseline cardiovascular medications.

Summary statistics will be obtained: frequency and percentage will be reported for categorical data; mean, standard deviation, minimum, maximum, median, the 1st and 3rd quartiles will be reported for continuous data.

7.7 Treatment Characteristics

After enrollment in the China Micra clinical study, at each protocol required follow-up, the investigator must assess for any AEs or medication changes and evaluate the study device to verify study device function.

7.7.1 Implant

Implant information will be collected on eCRFs for all enrolled subjects. For subjects with successful implants, variables to be summarized include, but are not limited to: device location, number of times engaged, anticoagulation, type of anesthesia, closure method, impedance, R-Wave measurement, auto decrement threshold, capture management threshold, and procedure durations (e.g. skin to skin, introducer in/out, etc.). Summary statistics will be obtained: frequency and percentage will be reported for categorical data; mean, standard deviation, minimum, maximum, median, the 1st and 3rd quartiles will be reported for continuous data.

For subjects with unsuccessful implant attempt, a listing will be compiled to summarize available information, including the reason(s) the implant attempt was unsuccessful.

The Micra implant success rate will be assessed on a per subject basis, calculated as the number of subjects successfully implanted with a Micra TPS divided by the total number of subjects with at least one implant attempt expressed as a percentage.

7.7.2 Pre-Hospital Discharge

Pre-hospital discharge information will be collected on eCRFs for all subjects with Micra implant attempt. Variables to be summarized include but are not limited to: duration of hospital stay,

and electrical data (impedance, R-Wave measurements, auto decrement threshold, and capture management threshold) and activity restrictions for successfully implanted subjects.

Summary statistics will be obtained: frequency and percentage will be reported for categorical data; mean, standard deviation, minimum, maximum, median, the 1st and 3rd quartiles will be reported for continuous data.

7.7.3 System Modification

In the event a system modification occurs, the data will be collected on the eCRFs. A listing will be compiled to summarize the system modification details. Information will include but is not limited to: reason for system modification, device repositioning, outcome of repositioning, extraction information, additional actions and electrical data.

7.8 Interim Analyses

There is no planned formal interim analysis for this study. However, descriptive summaries of the study data may be conducted as deemed appropriate throughout the study. All efforts will be made to ensure such descriptive analyses will not jeopardize the study final report. The final study analysis will be conducted after data collection is completed, verified and locked.

7.9 Evaluation of Objectives

7.9.1 Primary Objective

To demonstrate the Micra TPS is safe by estimating the Micra TPS implant procedure and/or system related major complications free survival probability through 6 months post implant.

7.9.1.1 Hypothesis

The primary endpoint is Micra TPS and/or procedure related major complications through 6 months (183 days) post implant. The corresponding statistical hypothesis for this study (utilizing single arm OPC design) is:

$$\begin{aligned} H_0 : S_T &\leq S_0; \\ H_1 : S_T &> S_0 \end{aligned}$$

Where S_T is the expected value of the probability of a subject free from Micra TPS and/or procedure related major complications through 6 months post implant; S_0 is the OPC. The objective will be considered met if the lower bound of the two-sided 95% CI for the estimate is greater than 83%.

7.9.1.2 Statistical Analysis Method

All subjects who undergo an Micra implant procedure will be included in the analysis. The Kaplan-Meier survival analysis will be used to estimate the probability of a subject free from Micra TPS and/or procedure related relate major complications. The log-log transformation will be used to calculate the 95% confidence limits.

Definitions:

- Endpoint event for the survival analysis is Micra TPS and/or procedure related major complications, defined as those AEs resulting in:
 - Death
 - Permanent loss of device function due to mechanical or electrical dysfunction of the device (e.g. pacing function disabled, leaving device abandoned electrically)
 - System revision (reposition, replacement, explant)
 - Hospitalization
 - Prolonged Hospitalization by 48 hours or more

The CEC will determine if the AE is related to Micra TPS and/or procedure; and if the AE is a major complication. **Note:** Only system or procedure-related AEs will be classified as a major complication, minor complication or an observation. In the event the CEC provides an "Unknown" classification relationship to the Micra TPS and/or procedure, the event will not be considered "Related" for the primary endpoint analysis. Refer to section 7.9.1.4 for additional information.

- Censoring occurs in subjects who do not experience any Micra TPS and/or procedure related major complications
- Follow-up time: from the date of Micra implant procedure to
 - the onset date of a Micra TPS and/or procedure related major complication, or
 - study termination date (e.g. subject exit, die, or study closure, etc.), or
 - the date of Micra deactivation due to any reason that is not related to the Micra TPS or procedure (e.g. device system upgrade, the subject's other comorbidities, etc.), or
 - the last follow-up date, if none of the above occurs.

The statistical analysis of the primary objective will be 2-sided, using 0.05 significance level. The statistical analysis software package SAS will be used to conduct these analyses.

A Kaplan-Meier survival analysis will be conducted to estimate the freedom from AEs classified as major complications that are related to the Micra TPS and/or procedure by the CEC within 6-months (183 days) post-implant. The Kaplan-Meier method is an appropriate method to analyze this endpoint as it enables inclusion of all subjects with an attempted implant. Additionally, the onset date of all Micra related major complications will be known to the nearest calendar day. Day of follow-up for subjects successfully implanted with the Micra TPS will be calculated as the minimum of the days from successful implant to: (1) onset date of a major complication related to the Micra TPS or procedure (if any), (2) study exit date (if exited), (3) death date (if death occurs), (4) 6-month follow-up visit (if completed), (5) last follow-up visit, or (6) 184 days. Subjects without a major chronic complication related to the Micra TPS and/or procedure during the follow-up period will be considered censored in the Kaplan-Meier analysis. Days of follow-up for subject who have only unsuccessful implant attempt(s) without being successfully implanted will be set to zero (0), unless a major complication occurs in which case the days of follow-up will be calculated from the date of unsuccessful implant attempt to the event onset date. The null hypothesis will be rejected in favor of the alternative if the lower boundary of the two-sided 95% CI is greater than 83%.

The 6-month (183 day) major complication freedom rate will be estimated using the Kaplan-Meier method with the log-log transformation to compute the two-sided CIs, [REDACTED]

[REDACTED]

[REDACTED]

[REDACTED]

Additionally, a corresponding one-sided p-value comparing the 6-month Micra procedure and/or system major complication freedom rate to 83% will be constructed using the formula:

$$z = \frac{\log(-\log(S(t))) - \log(-\log(0.83))}{\sqrt{\sigma(t)^2 / (S(t) * \log(S(t)))^2}}$$

Where $S(t)$ is the observed 6-month (183 days) freedom rate and $\sigma^2(t)$ is Greenwood's estimate of the variance of the survival function at time t . The one-sided p-value will then be computed from the standard normal distribution as $P(Z < z)$ [note this is the area of the standard normal distribution less than z since $\log(-\log(S(t)))$ will be more negative than $\log(-\log(0.83))$ if $S(t) > 0.83$].

[REDACTED]

